#### 4.2 TREATMENT PHASE

Subjects who meet all eligibility criteria, as per data gathered from Screening Visit and who stay eligible for the study are to be randomized and treated.

## 4.2.1 Treatment Visit-1 (T1)

Treatment Visit 1 (T1) will happen -2/-3 days prior to the transplant. The following assessments will be performed at the T1.

## **Pre-Treatment**

- Confirmation of eligibility criteria by reviewing test results and other criteria assessments performed at the Screening Visit (section 7.2)
- Any changes in concomitant medications (section 7.5)
- Any changes in medical history since Screening Visit (section 7.4),
- ECOG performance status (section 7.10)

12. ECG (section 7.7),

CONFIDENTIAL Page 59 of 108

- Collection of Blood Specimens for:
- o CBC w/diff (section 7.11.1)
- o Serum Biochemistry (section 7.11.2)
- Randomization (see section 7.12)

# Administration of Study treatment (PRO 140 or Placebo)

All eligible subjects who are randomized will receive either PRO 140 350 mg or placebo as subcutaneous injection in the abdomen. A total of 350 mg (175 mg/mL) is delivered as two 1 mL injections on opposite sides of the abdomen. The study treatment (PRO 140 or placebo SC injections) will be administered by a licensed medical professional (MD, DO, PA, LPN, LVN, NP, or RN).

### **Post-Treatment**

- Injection Site Reaction Assessment (see section 7.15)
  - ➤ **Note:** To assess injection site reactions, refer to the investigator injection site reaction table (refer to section 17.1).
- Injection Site Pain Assessment (VAS) (section 7.16)
- Vital Signs (see section 7.9) will be assessed within 15 minutes of study treatment administration.
- Assessment of Adverse Events (AE) (see section 9)

## 4.2.2 Treatment Visit-2 (T2) - Stem Cell Infusion (Day 0)

The following assessments will be performed on Treatment Visit-2:

- Assess for any Adverse Events and changes in Concomitant medications (section 9 and 7.5)
- Physical examination (section 7.6)
- Vital Signs (section 7.7)
- Collection of Blood Specimens for
  - o CBC (section 7.11.1)
  - Lymphocyte Phenotype Panel (section 7.11.4)
- Study Treatment Administration (PRO 140 or Placebo) (section 7.13)

CONFIDENTIAL Page 60 of 108

Date: 17 Jun 2016

- Stem cell infusion will be conducted post-study treatment administration (as per institutional guidelines; see section 7.19)
- Diagnosis and Grading of GVHD (section 7.17 and 7.18)
- Injection Site Reaction Assessment (section 7.15)
  - ➤ **Note:** To assess injection site reactions, refer to the investigator injection site reaction table (refer to section 17.1).
- Injection Site Pain Assessment (VAS) (section 7.16)

## 4.2.3 Treatment Visit-3 to Treatment Visit-11 (T11)

The following assessments will be performed at each visit, unless otherwise specified:

- Assess for any Adverse Events and changes in Concomitant medications (section 9 and 7.5),
- Diagnosis and Grading of GVHD (section 7.17 and 7.18)
- Physical examination (section 7.6) (at T8, T11)
- Vital Signs (section 7.9), (at T4, T6, T7, T8, T9, T10, T11)
- ECOG performance status (section 7.10) (at T4, T7, T9, T11)
- ECG (section 7.7) (at T6, T9, T11)
- Collection of Blood Specimens for:
  - o CBC w/diff (section 7.11.1)
  - o Serum biochemistry (section 7.11.2) (at T4, T6, T7, T8, T9, T10, T11)
  - Serum pregnancy test, for female subjects of childbearing potential (section 7.11.7) (at T7 and T11)
  - Anti-idiotypic antibodies to PRO 140 (section 7.11.6) (at T7 and T11)
  - Lymphocyte Phenotype Panel (section 7.11.4) (at T4, T6, T8 and T11)
  - o T-cell and myeloid chimerism (section 7.11.5) (at T6, T8 and T11)
- Collection of Urine Specimen for Urinalysis (section 7.11.8) (at T7 and T11)
- Study Treatment Administration (PRO 140 or Placebo) (section 7.13)
- Injection Site Reaction Assessment (section 7.15)

CONFIDENTIAL Page 61 of 108

Version 3.0 Date: 17 Jun 2016

- ➤ **Note:** To assess injection site reactions, refer to the investigator injection site reaction table (refer to section 17.1).
- Injection Site Pain Assessment (VAS) (section 7.16)

#### 4.3 FOLLOW-UP PHASE

## 4.3.1 Follow-Up Visit 1

The follow-up visit 1 will occur two (2) weeks after the last treatment visit. The following assessments will be performed at the follow-up visit 1, unless otherwise specified:

- Assess for any Adverse Events and changes in Concomitant medications (section 9 and 7.5),
- Vital Signs (section 7.9),
- ECOG performance status (section 7.10)
- Collection of Blood Specimens for
  - o CBC w/diff (section 7.11.1)
  - o Serum biochemistry (section 7.11.2)
- ECG (section 7.7)
- Grading GVHD skin, gut, liver (section 7.17)

### 4.3.2 Follow-up Visit 2

The follow-up visit 2 will occur one year after the first treatment visit. The following assessments will be performed at the follow-up visit 2, unless otherwise specified:

- Assess for any Adverse Events and changes in Concomitant medications (section 9 and 7.5),
- Vital Signs (section 7.7),
- Collection of Blood Specimens for:
  - o T-cell and myeloid chimerism (section 7.11.5).

CONFIDENTIAL Page 62 of 108

### 5 SUBJECT COMPLETION AND WITHDRAWAL

#### 5.1 SUBJECT COMPLETION

A subject who completes the 14-week Treatment Phase and 2-week Follow-Up Phase will be considered as having completed the study.

### 5.2 SUBJECT WITHDRAWAL

A subject who is randomized but does not complete the study, as defined in section 5.1, is considered to have prematurely withdrawn from the Study.

All subjects have the right to withdraw at any point during treatment without prejudice to future care. It will be documented whether or not each subject completed the clinical study. If for any subject, study treatment or observations were discontinued, the reason(s) will be recorded.

The Investigator can discontinue a subject at any time if it is considered medically necessary.

In addition, subjects WILL be withdrawn from the study, in consultation with the Medical Monitor and the Investigator, if any of the following are met:

- A subject is significantly non-compliant with the requirements of the protocol.
- The investigator determines that it is in the best interest of the subject.
- Subject chooses to withdraw or is withdrawn due to an adverse event specified in section 9.1.9
- A subject becomes pregnant

**Note**: The pregnancy will be followed to term for safety follow-up. Relevant safety information collected after the study has completed will be reported as supplemental information.

• Discontinuation of study by Sponsor

[figure not shown]
Premature withdrawal from the study MAY occur if, in consultation with the Medical Monitor and the Investigator, any of the following are met:

- A subject is treated with a prohibited medication
- Major protocol violation

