### 4 STUDY SCHEDULE

This research study is divided into three study phases:

- (1) Screening Phase (Screening to T1 Visit) begins with signing of Informed Consent and lasts up to 4 weeks (28 days).
- (2) Treatment Phase (up to 14 weeks ± allowed windows). Eligible subjects will be randomized and receive up to 11 study treatments (PRO 140 or placebo), given on Day -3 or Day -2 prior to stem cell infusion, on the day of stem cell infusion (Day 0), and then weekly for 30 days (at Week 1, Week 2, Week 3 and Week 4) after which it will be administered every two weeks for up to 98 days (at Week 6, Week 8, Week 10, Week 12 and Week 14).
- (3) Follow-Up Phase (up to one year). Subjects who have completed the Treatment phase or who have withdrawn from the study will be followed-up at 2 weeks after the last treatment visit and one year after first treatment visit.

Procedures to be performed during each of these study phases are described below and provided as a Schedule of Assessments in Table 4-1.

CONFIDENTIAL Page 54 of 108

Table 4-1: Schedule of Assessments

iis	iV bəlub	əųəsu	n						×	×	×	×		×	×				
p Phase le year)	Follow-up Visit 2	52	Day 365±14							×						X			
Follow-Up Phase (up to one year)	Follow-up Visit 1	16	Day 112±3							X	X		X	×	X	X			
	T11	14	Day 98±3						×	×	×		X	×	X		X	×	X
	T10	12	Day 84±3							×				×	X	X			
	T9	01	Day 70±3							×	×		X	×	X				
	T8	œ	Day 56±3						X	X				×	X	X			
Phase	T7	9	Day 42±3							X	X			×	X		X	X	X
Treatment Phase (14 weeks)	9L	4	Day 28±3							X			X	×	X	X			
Tre	TS	e	Day 21±3											X					
	T4	2	Day 14±3							×	×			×	Х				
	T3	-	Day 7±3											×					
	T2		Day 0						×	×				×					
	T.1		Day -3/- 2			×	×			×	×		X	×	X	X			[6]X
Screening Phase (up to 4 weeks)	Screening Visit	Up to -4 weeks	Up to -28 days		×	×	×	×	×	×	×	X	X	×	X	X	X	×	
				Protocol Section	Section 7.1	Section 7.2	Section 7.4	Section 7.3	Section 7.6	Section 7.9	Section 7.10	Section 7.9	Section 7.7	Section 7.11.1	Section 7.11.2	Section 7.11.3	Section 7.11.8	Section 7.11.7	Section 7.11.6
Study Phase	Visit	Weeks	Days	Procedures	Informed Consent 	Eligibility Evaluation 	Medical History 	Subject Demographic	Physical Examination	Vital Signs 	ECOG performance score	Height and Weight	ECG	Complete Blood Count (CBC) 	Serum Biochemistry 	ЬРК	Urinalysis 	Serum Pregnancy Test 	Anti-idiotypic antibodies to PRO 140

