Page 55 of 108 CONFIDENTIAL

tisi	iV bəlub	əyəsu	n							X	X		X	×
Follow-Up Phase (up to one year)	Follow-up Visit 2	52	Day 365±14				X						X	X
Follow-Up Phas (up to one year)	Follow-up Visit 1	16	Day 112±3							X			X	X
	T111	14	Day 98±3			×	×		×	X	X	X	X	X
	T10	12	Day 84±3						×	X	X	X	X	X
	L19	10	Day 70±3						×	X	X	X	X	X
	T8	8	Day 56±3			×	×		×	X	X	X	X	X
Phase ks)	41	9	Day 42±3						X	X	X	X	X	X
Treatment Phase (14 weeks)	9L	4	Day 28±3			X	X		X	X	X	X	X	X
Tr	TS	3	Day 21±3						X	X	X	X	X	X
	T4	2	Day 14±3			X			X	X	X	X	X	Х
	Т3	1	Day 7±3						×	X	X	X	X	X
	T2		Day 0			×			×	X 	×	×	X	×
	TI		Day -3/-					×	×		X		X 	X
Screening Phase (up to 4 weeks)	Screening Visit	Up to -4 weeks	Up to -28 days		×									X
				Protocol Section	Section 7.8	Section 7.11.4	Section 7.11.5	Section 7.12	Section 7.13	Section 7.17	Section 7.15	Section 7.16	Section 9.1	Section 7.5
Study Phase	Visit	Weeks	Days	Procedures	HIV rapid antigen test	Lymphocyte Phenotype Panel	T-cell and myeloid chimerism	Randomization	Administration of PRO 140 or Placebo	Grading GVHD – skin, gut, liver 	Injection Site Reaction Evaluation	Injection Site Pain Assessment (VAS) 	Adverse Events	Prior and Concomitant Meds

Informed consent must be obtained prior to patient participation in any protocol-related activities that are not part of routine care.

Initial evaluation of patient eligibility will be performed by Investigator.  $\overline{2}\overline{2}\overline{2}$ 

Medical history, past surgeries, disease history, history of substance abuse, social history will be recorded as Medical History up to the first randomized Treatment at Visit T1

4 5 9

Post treatment vital signs will be recorded (sitting blood pressure, heart rate, respiration rate, and temperature)
Hemoglobin, Hematocrit (HCT), Red Blood Cells (RBC), White Blood Cells (WBC) with total and differential count, Absolute Neutrophil Count (ANC) and platelets

Serum Biochemistry:

Hepatic function indicators: total and direct bilirubin, alkaline phosphatase (ALP), aspartate aminotransferase (AST), alanine aminotransferase (ALT), total

[figure not shown]

Version 3.0 Date: 17 Jun 2016

protein, Lactate dehydrogenase (LDH)

- Renal function indicators: Blood Urea Nitrogen (BUN), creatinine
  - Electrolytes: sodium, potassium, chloride, calcium and bicarbonate
    - Other: glucose (random), cholesterol (total)

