# 9.1.8 SC Injection-related Events

SC and IV injections of concentrated protein materials can be associated with injection-related AEs that impact the ability to safely and successfully deliver the drug. Local injection-site reactions may include pain/discomfort, induration, erythema, nodules/cysts, pruritis, ecchymosis, etc. For SC injections, bleeding, absorption of the drug, leakage of drug, and induration at the local injection site can be additional complications. Other AEs that are common to monoclonal antibody-based therapies are chills, headache, backache, malaise, fever, pruritis, rash, nausea, tingling, and hypertension.

SC Injection-site reactions thought to be directly related to the injection are considered to be AEs of special interest, and a separate guideline for the acquisition of data related to this AE of special interest is provided in section 17.1.

# 9.1.9 Stopping Rules for PRO 140

Subjects who develop Grade 1 or Grade 2 adverse events will continue per protocol. If a subject chooses to discontinue study treatment, the site should notify the protocol team leadership, and encourage the subject to complete any remaining study visits until the toxicity resolves.

For subjects who develop Grade 3 or higher adverse events per below, or experience graft failure or relapse the study treatment will be permanently discontinued:

- Grade 3 or higher liver toxicity not attributable to other causes such as infection, GVHD or Sinusoidal Obstruction Syndrome (SOS);
- Grade 3 or higher toxicity which is assessed by the investigator to be definitely, probably or possibly related to the study drug;
- Graft failure or relapse;

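### A section 9.1.9 event ends only study drug in one place but appears under study withdrawal in another, so GVHD grading to Day 100 is not assured for early stoppers

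*Protocol*

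**What the plan says.** **Stopping drug.** Protocol section 9.1.9 covers listed Grade 3 or higher toxicity. For those subjects, and for those who "experience graft failure or relapse the study treatment will be permanently discontinued", only the treatment is ended.

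**Leaving the study.** Section 5.2 has a list headed by a statement that subjects will be withdrawn from the study. One bullet reads: "Subject chooses to withdraw or is withdrawn due to an adverse event specified in section 9.1.9". Section 5.1 defines completion: "A subject who completes the 14-week Treatment Phase and 2-week Follow-Up Phase will be considered as having completed the study". Under section 5.2, a randomised subject who does not meet that definition "is considered to have prematurely withdrawn from the Study". Neither section says whether attending the visits without dosing counts as completing.

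**Follow-up.** Under section 4, item 3, subjects who finished treatment or "who have withdrawn from the study will be followed-up at 2 weeks after the last treatment visit", and again one year after the first treatment visit. Section 4.3.1 uses the same two-week anchor and includes GVHD grading; section 4.3.2 (one year) does not. In Table 4-1 the row "Grading GVHD – skin, gut, liver" is marked at T2 to T11, Follow-up Visit 1 and unscheduled visits, and Follow-up Visit 1 is fixed at Day 112±3.

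**Follow-up off drug.** Section 5.2.1 is titled for withdrawn subjects, but it says that patients taken off treatment go on being followed under the protocol where that is feasible. Exclusion 1 removes patients who are not expected to be available for at least 114 days after transplant.

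**Analysis.** SAP 6.1 makes ITT the primary population, SAP 7.3 imputes nothing, and SAP 7.4 plans a tipping point analysis.

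**The concern.** The same event is given two consequences. Section 9.1.9 takes the subject off drug; section 5.2 names it under withdrawal from the study. The difference matters because section 4, item 3, is the sentence that sets follow-up for withdrawn subjects, and it offers them one more graded visit, timed from the last treatment visit and not from transplant.

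The term last treatment visit is not defined for someone off drug. T3 to T11 are all named treatment visits and include dosing, so it could mean the last dosed visit or the last T visit attended. No sentence says that an off-drug subject keeps the Table 4-1 grading calendar. With up to 20 sites, practice could differ.

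At stake is whether the endpoint can be observed over its fixed 100-day window. A Grade II–IV onset after the last scheduled grading would be missed, or graded only if an unscheduled visit took place. The SAP does not say how a subject without grading to Day 100 is counted. A tipping point analysis can show that a result is fragile, but it cannot recover ungraded days.

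**Working it through.** **The plan's own figures.** Table 4-1 has T11 on Day 98, and 98 + 14 = 112, which is the tabulated Follow-up Visit 1. The two anchors therefore agree for a subject dosed to T11, and differ if the two weeks are counted from an earlier last dose. The only precision figure (SAP section 4: 50% against 15%, 30 per arm) also reproduces: 0.35 ± 1.96 × √(0.50×0.50/30 + 0.15×0.85/30) = 0.35 ± 0.22, or 0.13 to 0.57. It takes all 30 per arm as evaluable.

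**Inputs.** Endpoint horizon: Day 100 (Protocol 8.2.1). Dose days: −3 or −2, 0, 7, 14, 21, 28, 42, 56, 70, 84, 98 (Protocol 7.13). Grading days: 0, 7, 14, 21, 28, 42, 56, 70, 84, 98, 112 (Table 4-1).

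**Dose-anchored reading** (section 4, item 3, and 4.3.1, with the last dosed visit as the last treatment visit):
- Last scheduled grading = last dose day + 14.
- Gap = 100 − (last dose day + 14).
- Gradings lost = Table 4-1 gradings after that visit, through Day 98.
- Visits added by the fix = Table 4-1 gradings after the last dose through Day 112, less any that falls on last dose + 14.

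| Last dose (day) | Last scheduled grading (day) | Gap to Day 100 | Gradings lost | Visits added by fix |
|---|---|---|---|---|
| −3 / −2 (T1 only) | 11 / 12 | 89 / 88 | 8 | 11 |
| 0 | 14 | 86 | 7 | 9 |
| 7 | 21 | 79 | 6 | 8 |
| 14 | 28 | 72 | 5 | 7 |
| 21 | 35 | 65 | 5 | 7 |
| 28 | 42 | 58 | 4 | 5 |
| 42 | 56 | 44 | 3 | 4 |
| 56 | 70 | 30 | 2 | 3 |
| 70 | 84 | 16 | 1 | 2 |
| 84 | 98 | 2 | 0 | 1 |
| 98 | 112 | none | 0 | 0 |

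In the T1-only row, the 8 lost are Days 14, 21, 28, 42, 56, 70, 84 and 98. The 11 added are those 8 plus Days 0, 7 and 112; none falls on Day 11 or 12.

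The Day 84 row is weak. Its visit falls on Day 98, the nominal day of T11, so no scheduled grading before Day 100 is lost. With the ±3-day window on the dose (Day 81 to 87), the visit falls on Day 95 to 101 and the gap runs from 5 to −1 days.

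**Calendar reading** (section 5.2.1 as the full Table 4-1 schedule). The last grading is at Day 112±3, that is Day 109 to 115, or 9 to 15 days after Day 100. The gap is zero for every early stopper.

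**Scale only.** If a subject with a missed event stays in as a non-event, one event is 1/30 = 3.3 percentage points in an arm. That holds for any missed event, whatever the cause. It is not an estimate of what this wording would do.

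**The case against.** The strongest reply is that the protocol already intends follow-up off drug. Section 5.2.1 says so and also asks for every attempt to obtain follow-up information. Exclusion 1 looks beyond Day 100. Section 5.2 records discontinuation of treatment and of observations as separate things. The T visits have fixed days, the last being Day 98, so two weeks after the last treatment visit is naturally Day 112. Table 4-1 allows grading at unscheduled visits, and adverse events are collected to the final study visit, so late GVHD need not vanish from the record.

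Most of this stands. It makes the calendar reading at least as plausible as the other, and on it nothing is lost. It does not close the question: following someone under the protocol includes following section 4, item 3; the section 5.2.1 commitment is qualified by feasibility; and unscheduled grading or adverse event reporting does not replace scheduled grading.

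A reader might infer that section 5.2 obliges sites to withdraw every subject with a 9.1.9 event and so cuts off grading. The documents do not support that. The bullet is circular, since it lists being withdrawn as a ground for withdrawal, and section 9.1.9 speaks only of treatment.

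A reader might also take the advice in section 9.1.9 to "encourage the subject to complete any remaining study visits until the toxicity resolves" as limiting follow-up after a Grade 3 event. It stands in the paragraph that begins "Subjects who develop Grade 1 or Grade 2 adverse events will continue per protocol" and concerns subjects who choose to stop. It does, however, name an end point other than Day 100.

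**Conclusion.** The conflict is in the text and should be fixed. Sections 9.1.9 and 5.2 attach different consequences to the same event, and section 4, item 3, with 4.3.1 and Table 4-1 leaves open whether a subject off drug is graded to Day 100.

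The size depends wholly on the reading. The nominal gap is 2 to 89 days if grading is timed from the last dose, with the 2-day end of little consequence, and zero if the Table 4-1 calendar continues. The first figure assumes that the site treats the subject as withdrawn, or otherwise applies the two-week rule, and takes the last dosed visit as the last treatment visit.

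A reader might go further and infer that the treatment comparison is biased. The documents do not support that: they give no stopping rate and nothing on how stopping would differ between arms in a double-blind trial, so neither the number affected nor the direction of any effect can be derived. The case for acting is that ungraded days cannot be recovered later and the clarification is cheap. Confidence is moderate, because the sponsor may already intend the calendar reading.

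**What to change.** 1. Reword the section 5.2 bullet so that a 9.1.9 event, including graft failure or relapse, ends study treatment only.
2. State in section 4 (item 3), 4.3.1 and 5.2.1 that every randomised subject who stops drug without withdrawing consent keeps GVHD grading, undosed, on the Table 4-1 transplant-day calendar through Day 98 and Day 112±3.
3. Align the section 9.1.9 wording that ties remaining visits to resolution of the toxicity.
4. Keep the safety assessment two weeks after the last dose. It falls on a calendar visit for every last dose from Day 0 to Day 98 except Day 21 (Day 35). For a T1-only subject it falls on Day 11 or 12.

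The other withdrawal grounds in section 5.2 can stay as the sponsor prefers.

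**Cost.** A short amendment. Against the dose-anchored reading, each early stopper gains 1 to 9 undosed grading visits for last doses on Day 84 back to Day 0, and nominally 11 if dosed only at T1. Against the calendar reading, the only addition is the two-week safety visit where it misses a calendar day. The grading form and the assessor do not change.

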## 5.2.1 Data Collected for Withdrawn Subjects

Investigators considering discontinuing study treatment should contact the medical monitor prior to such discontinuation. Patients who have study treatment discontinued will continue to be followed, per protocol, whenever possible. Patients who have study treatment

CONFIDENTIAL Page 63 of 108

discontinued due to a serious adverse event will be followed until resolution or stabilization of the event.

In the event that a subject is withdrawn from the study at any time due to an adverse event or serious adverse event (SAE), the procedures stated in Section 9.1.1 or 9.2.1, respectively must be followed.

Every attempt should be made to collect follow-up information. The reason for withdrawal from the study will be recorded in the source documents and on the appropriate page of the eCRF.

Before a subject is identified as lost-to-follow up, the site should make all reasonable efforts to contact the subject. These attempts must be documented and should include at a minimum one phone call and one certified letter.

### 5.3 SCREEN FAILURES

A subject who has signed a consent form, has been assigned a screening number, but is not randomized is classified as a screen failure. Subject number, demographics and reason for screen failure will be recorded.

If a subject initially fails to meet inclusion/exclusion criteria and is later reconsidered for participation, the subject will be re-consented and assigned a new screening number at the time of re-screening. Subjects who fail their first screening attempt may be re-screened only one more time (i.e., up to two screenings) and may be enrolled if they are found to meet all inclusion and no exclusion criteria at the subsequent screening visit.

CONFIDENTIAL Page 64 of 108

